
**Overview of sample size computations:** Power computations were performed using the Stata power command. To determine the required sample size for the study, we determined the hypotheses for which we require the largest sample size. In this study, Aim 2 requires the largest sample size (n=56 with complete data; N=62 total randomized). We conducted the power analysis for Aims 1 assuming the sample size of N=56 required to address Aim 2. Given the exploratory nature of Aim 3, these tests were not considered in determining the required sample size for the overall study.

4.6b. Data Analysis and Sample Size Calculation for Aim 1: This aim examines the efficacy of the BEST program on PAP adherence. The main outcome will be the proportion of nights (out of 30 nights) with >4 hours of PAP use, as measured by the PAP machine itself. PAP adherence will be computed for the first 30 days (month 1), and for each subsequent 30-day period (months 2-12). All participants will be measured for at least 180 days, thus providing at least 6 months of data for all participants. PAP adherence rates beyond month 6 will be computed for participants who enrolled early enough to provide such data. Because adherence data will be gathered remotely using existing telemonitoring technologies in which PAP machines transmit use data to a cloud-based server, complete data is expected for each person. In an ongoing VA-funded study of PAP adherence being conducted by [name] research group, PAP adherence data or confirmed non-use has been obtained in 100% of participants using this method. The proportion of nights a patient uses PAP for 4 or more house will be computed by summing nightly scores (1=PAP used at least 4 hours; 0=PAP used less than 4 hours) and dividing the sum by the number of observations (i.e., 30 nights). Denoting  $\hat{p}_{ij}$  as the proportion of nights for person "i" in month "j", the sampling distribution of  $\hat{p}_{ij}$  will have an expected value equal to  $p_i$  (the true proportion who use PAP in the population in month "i") and the standard deviation of this sampling distribution is equal to  $sqrt(N*p_i *(1-p_i))$ . Further, based on the central limit theorem the sampling distribution of these monthly proportions,  $\hat{p}_i$  is expected to be normally distributed, justifying the use of normal theory statistical methods for the analysis of monthly PAP adherence.

[figure not shown]

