Mixed-effects models will be used to compare monthly PAP adherence rates for the BEST program versus control program. When applied to longitudinal designs, mixed-effects models accommodate incomplete data across time points (such as arises in this study where only some participants will have data beyond six months) and can permit specification of a wide variety of residual covariance structures. PAP adherence will be analyzed using a 2 by 12 factorial mixed-effects model with a fixed intercept, where treatment group is a two-level between subjects factor (i.e., BEST versus control) and time is a 12 level categorical repeated measures factor (i.e., month 1, month 2, ... month 12). This approach will allow us to examine potential non-linear trends in the data which would not be readily apparent if time were treated as a continuous variable. The Bayesian Information Criteria (BIC) will be used to identify and select the best fitting residual covariance structure. Using the mixed-effects model, the difference in adherence rates between the BEST program and control group will be assessed and tested at each month.

Hypothesis 1a will be assessed evaluating the significance of the difference in adherence rates between the BEST program and control groups in months 1-3 (during the BEST program intervention).

Hypothesis 1b will be assessed by testing the significance of the difference in adherence rates between the BEST program and control groups in months 4-6 (after the BEST program has ended).

**Figure 6** illustrates four possible patterns of results Pattern 1 suggests the BÉST program immediately improved PAP adherence and effects were sustained over time. Pattern 2 shows that the BEST program improved PAP adherence during the treatment period; however, effects later diminish. Pattern 3 shows that the

BEST program improved PAP adherence gradually during the "treatment" period and effects were sustained over time. Pattern 4 also shows that the BEST program improved PAP adherence gradually; however, effects later diminished, These patterns will be statistically dissected to distinguish between immediate vs. gradual gains in pap adherence during the "treatment" phase, and between "sustained" and "diminishing" effects during the posttreatment phase (refer to [name] 2012).

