Hypothesis 1c will be assessed by testing the significance of the difference in the adherence rates between the BEST program and control groups in months 6-12. Further analyses will be performed by graphically representing the results (as illustrated **Figure 6**: Possible patterns of results illuminated by the proposed analysis. in **Figure 6**, with 12 instead of 6

months), and further analyses of treatment maintenance versus diminution of effects will be statistically considered.

**Power Analysis for Hypotheses 1a-c:** As described above, the power with respect to Aim 1 was computed assuming a sample size of N=56 with complete data (required to address Aim 2; total N=62). This aim focuses on the difference between the two groups in terms of the average proportion of nights of PAP use  $\geq$ 4 hours per month. The standard deviation (SD) of this proportion is most conservatively estimated as SD= 0.0913 [computed as sqrt(.5\*(1-.5)/30)=.0913]. Given this SD, alpha=0.05 and power=.80, the study can detect a difference in the average proportion of nights of PAP use  $\geq$ 4 hours of 7% between intervention and control for a given month. In interpreting the results, however, we will focus on larger more clinically-important effects. This study will have ample power to detect these. For example, using the same sample size and alpha, the power to detect a 10% difference between groups would be power=.98. The power to detect a 20% difference would exceed power=.999. We would consider a difference of less than 10% (even if statistically significant) not clinically meaningful. We would consider a difference of 10% or more to be a clinically relevant difference. We would consider a difference of 30% or more to be a substantial and very clinically meaningful difference.

**4.6c. Data analysis and Sample Size Calculation for Aim 2:** This aim compares outcome measures beyond PAP use that are expected to improve as a result of the BEST program, compared to the control program. The outcome variables tested will include patient-reported sleep quality (hypothesis 2a), overall functioning (hypothesis 2b), quality of life (hypothesis 2c), and respiratory function (hypothesis 2d).

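### The Aim 1 power calculation uses one patient's night-to-night noise as the SD and leaves out variation between patients, so the 7% detectable difference and .98 power at 10% are unsupported

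*Protocol*

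**What the plan says.** Protocol section 4.6b (Power Analysis for Hypotheses 1a-c) states: "The standard deviation (SD) of this proportion is most conservatively estimated as SD= 0.0913", with sqrt(.5*(1-.5)/30) shown as its source. With 56 complete patients, alpha 0.05 and 80% power, it derives a detectable difference of 7% in a given month. It adds that "the power to detect a 10% difference between groups would be power=.98" and that power at 20% exceeds .999. The same paragraph sets the clinical yardstick: "We would consider a difference of 10% or more to be a clinically relevant difference".

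Earlier in 4.6b, the expected value of a patient's monthly proportion is described as "the true proportion who use PAP in the population in month". Under the mixed-effects model, "the difference in adherence rates between the BEST program and control group will be assessed and tested at each month". The SAP (Data Analysis for Aim 1) replaces this with a two-sample t-test on nights of use out of 90 and gives no power figure.

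On sample size, the protocol's overview says "we determined the hypotheses for which we require the largest sample size" and concludes that "Aim 2 requires the largest sample size". For the later months, "PAP adherence rates beyond month 6 will be computed for participants who enrolled early enough to provide such data".

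**The concern.** The quantity sqrt(p(1-p)/30) describes how far one patient's observed 30-night proportion would scatter around that patient's own true rate. A comparison of two groups of patients has a second source of variation: patients have different true rates. Choosing p=0.5 maximises the first component, but the second is absent. The mixed model does not remove it from a between-group contrast. No baseline covariate can absorb it either, because Table 6 has no pre-treatment PAP adherence measure.

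At stake is how an inconclusive result is read. Adherence is the main Aim 1 outcome. A null result set beside a claimed power of .98 would be taken as evidence against a 10-point benefit, when the real chance of detecting one may be well below one half. The statement that Aim 2 is the most demanding aim also depends on this SD.

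**Working it through.** **Inputs.** 28 per group (section 4.6a), alpha 0.05 and SD 0.0913 (section 4.6b). Two-sided testing is stated only for Aim 2 and is assumed here for Aim 1; the reproduction supports it. Power is from the two-sample t-test (noncentral t, 54 df).

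**Step 1: reproduce the stated figures.** SD = sqrt(0.25/30) = 0.0913. The standard error of the difference is 0.0913 × sqrt(2/28) = 0.0244. The detectable difference at 80% power is 6.96 points. Power is .981 at 10 points and above .999 at 20. All three stated figures are recovered. One-sided testing would give .993 at 10 points (normal approximation), so the protocol used a two-sided test. The arithmetic is right; the input is at issue.

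**Step 2: add variation between patients.** Let s be the SD of patients' true use rates, p the mean rate and m the number of nights, with nights independent given the patient's rate:

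total SD = sqrt( s² + (p(1-p) - s²)/m )

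With s=0, p=0.5 and m=30 this is 0.0913. Any s above zero increases it. Example at s=0.20: sqrt(0.04 + (0.25-0.04)/30) = sqrt(0.047) = 0.2168, more than twice the stated value.

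**Step 3: results.** The documents give no s, so the range is an assumption (p=0.5, 28 per arm).

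| s | Total SD, 30 nights | Detectable difference (points) | Power at 10 points | at 20 | at 30 |
|---|---|---|---|---|---|
| 0 (as stated) | 0.0913 | 7.0 | .98 | >.999 | >.999 |
| 0.05 | 0.104 | 7.9 | .94 | >.99 | >.99 |
| 0.10 | 0.134 | 10.2 | .78 | >.99 | >.99 |
| 0.15 | 0.173 | 13.2 | .56 | .99 | >.99 |
| 0.20 | 0.217 | 16.5 | .40 | .92 | >.99 |
| 0.30 | 0.309 | 23.5 | .22 | .66 | .95 |
| 0.40 | 0.404 | 30.8 | .15 | .44 | .78 |

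Power drops below .80 at s of about 0.096 for 10 points, 0.25 for 20 and 0.39 for 30. The stated >.999 at 20 points holds only up to s of about 0.115.

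**Step 4: scale of s.** With beta-distributed rates and mean 0.5, s=0.10 puts the middle 80% of patients at 37-63% of nights, s=0.20 at 23-77% and s=0.30 at 8-92%. As a second illustration, suppose one of 28 patients per arm never uses PAP, the rest are identical and the mean is 0.5. Then s = 0.5 × sqrt(1/27) = 0.096, which alone brings power at 10 points from .98 to about .80. Two such patients give s = 0.5 × sqrt(2/26) = 0.139 and power of about .61. The protocol gives no non-use rate, though it does refer to confirmed non-use in a related study.

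**Step 5: the SAP's 90 nights.** Only the night-to-night part shrinks (to 0.0527 at s=0). At s=0.05 the detectable difference is 5.5 points and power at 10 points is .999. At s=0.10, 0.20, 0.30 and 0.40, power at 10 points is .90, .43, .23 and .15. The .80 limit moves from about 0.096 to about 0.12.

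**Step 6: sensitivity.** With all 62 patients contributing (31 per arm, 30 nights), power at 10 points is .82, .43, .24 and .16 at s=0.10, 0.20, 0.30 and 0.40. With mean use 0.3 or 0.7 instead of 0.5, it is .405 at s=0.20 and .224 at s=0.30.

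**Step 7: which aim needs most patients.** For 80% power at 10 points with 30 nights, Aim 1 needs 15 per arm at s=0, 30 at s=0.10, 75 at s=0.20 and 151 at s=0.30. Aim 2 was given 28.

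**The case against.** The best defence concerns consequence rather than correctness.

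- **N=62 was derived from Aim 2.** The Aim 1 figures were then computed at that N, and 10 points is a relevance threshold, not a declared design target. The protocol says interpretation will focus on larger effects. Power stays at or above .80 up to s of about 0.25 for 20 points and 0.39 for 30 points. This stands and limits the damage.
- **The size of the shortfall rests on an assumed s.** True: nothing in the documents favours 0.20 over 0.05. But the stated monthly figures require s close to zero, and no support for that is offered.
- **The SAP's 90-night outcome is more forgiving.** Also true. It reaches a total SD of 0.0913 at s of about 0.075, and below that does better than the protocol claims. The SAP makes no power claim, however, and the protocol's claim is for a given month.
- **The text of 4.6b is not conclusive on a common rate.** The subscripts there conflict and one could be read as patient-specific. Likewise, choosing a residual covariance structure by BIC does not commit the plan to correlated months. Neither point is needed: the printed formula contains no between-patient term.
- **The varying N after month 6 is disclosed and is a separate matter from the SD.** Correct, but the power paragraph still covers Hypotheses 1a-c at N=56.

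**Conclusion.** The concern holds. The SD of 0.0913 omits between-patient variance and, at mean use 0.5 with independent nights, is the lower limit of the monthly SD. Calling it conservative is the wrong way round. The 7% detectable difference, the .98 and the >.999 are correct arithmetic on an unsuitable input. At 10 points and 30 nights, power is .78 to .22 for s from 0.10 to 0.30, and the detectable difference is 10.2 to 23.5 points. The claim that Aim 2 needs the largest sample fails at a 10-point target once s exceeds about 0.10.

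These sizes rest on an assumed s, mean use near 0.5, 28 per arm and nights independent given the patient's rate. The planned analyses use the observed variance, so estimates, type I error and confidence intervals are not biased. Because the claim concerns the main Aim 1 outcome at the protocol's own relevance threshold, it must be corrected.

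**What to change.** In section 4.6b, replace 0.0913 with an observed total SD across patients: of the 30-night proportion for the monthly contrasts, and of the 90-night proportion for the SAP outcome. The research group's ongoing PAP study (n=52 at the time of writing) is one possible source. It enrols older Veterans, so transfer to SCI/D is uncertain, and the documents do not say whether its data can be used here; show a range in any case. Remove the description as conservative and the .98 and >.999 figures. Suggested wording:

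> The total SD of the monthly proportion across patients was estimated as X from [source]. With 28 per group the detectable difference at 80% power is Y points; power at 10, 20 and 30 points is A, B and C. Results for total SDs from 0.09 to 0.40 are also shown.

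In the sample size overview, qualify the statement about Aim 2: at a 10-point target it holds only if s is below about 0.10. For Hypothesis 1c, state that the N=56 power does not apply to months 7-12, when only early enrollees contribute.

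The cost is one recalculation, access to nightly data from a comparable cohort (or the range alone if that is not available), and a few sentences. No planned test changes and no patients are added. The price is a less favourable power statement, possibly conceding that a 10-point difference cannot be detected reliably.

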The Spinal Cord Independence Measure-Self Report (SCIM-SR) will be used to evaluate performance of activities of daily living. The SCIM-SR is a self-report version of the SCIM III, a reliable and valid measure of global disability for patients with SCI/D. The SCIM–SR has 3 subscales: self-care, respiration and sphincter management, and mobility. Scores range from 0-100 and higher scores reflect greater independence. Comparison of the SCIM-SR to the SCIM III showed high correlations between the scales (Pearson's r for the total score=.87; subscales=.81-.87). Since some individuals' in the study will require the assistance of family members or caregivers, for descriptive purposes we will also ask an individual familiar with the patient's level of functioning to complete the SCIM if the patient gives permission for us to do so. The SCIM-SR total and subscales scores (as completed by the patient) will be used as the functional status outcome measure.

The WHOQOL-BREF is a 26-item version of the WHOQOL-100, and is frequently used as an outcome measure in clinical trials. The questionnaire is composed of four domains: physical health, psychological health, social relationships and environment. It also includes one question on overall quality of life and one on general health. Importantly, items on this scale are not dependent on mobility, which is unlikely to change in patients with

SCI/D as a result of improved sleep. The WHOQOL-BREF scores correlate highly (.89 or above) with WHOQOL-100 scores, and demonstrate good discriminant validity, content validity, internal consistency and test-retest reliability. The four WHOQOL-BREF domain scores will be used as main outcome measure.

The Patient Health Questionnaire-9 (PHQ-9) is a 9-item depression module in the PHQ (a self-administered diagnostic instrument for common mental disorders) which is part of the Primary Care Evaluation of Mental Disorders (PRIME-MD) suite of evaluation tools. The PHQ-9 aligns to the DSM-IV diagnostic criteria for depression and is widely used to screen for depression across VA. The PHQ-9 total score will be used to measure depressive symptom severity as an outcome.

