### 4.6. Data analysis plan:

**4.6a. Study Design Considerations:** The study design and data analysis will follow the CONSORT criteria for randomized controlled trials (RCTs). Participants will be randomly assigned to the treatment or control group as described in **Section 4.4b**. Randomization should produce groups that differ only by chance at baseline; nevertheless, the adequacy of randomization will be assessed by comparing the groups on all outcomes as measured at baseline. We will follow intention-to-treat (ITT) principles. While we anticipate some participants will not complete the intervention; we will continue to collect follow-up data from all randomized patients whether or not they complete the intervention program to which they are assigned. We anticipate no more than 10% of participants will have missing or incomplete follow-up data. To improve retention and reduce the risk of missing data, participants will be offered monetary incentives for completing follow-up assessments, regardless of whether they complete the intervention. In our recent studies of Veterans with disabilities, we were able to obtain follow-up data for up to 6 months in 92% of randomized participants. We have achieved this high follow-up rate by developing strong relationships with study participants, keeping them engaged and invested in the project, and making necessary accommodations to gather outcome data. While we do not anticipate differential attrition, we will compute the completion rate for each group (BEST and control) and compare completion rates to determine test for differences as a function of group. We will also compare baseline characteristics among those who have complete versus incomplete follow-up data to test for systematic attrition. To preserve the equivalency formed by randomization, ITT analyses will include all randomized participants for hypothesis testing. Since ITT analysis requires complete data, missing data will be imputed using multiple imputation. Sensitivity analyses will be performed comparing the ITT (with imputation) results to results for those with complete data (anticipated N=56). We have allowed for a 10% missing data rate in sample size computations. We anticipate randomizing 62 individuals (31 per group) to achieve a final total sample with complete outcome data at the 3-month followup of N=56 (28 per group). We do not anticipate additional attrition after 3 months since follow-up data beyond that time point will be gathered with remote telemonitoring.

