**Data Analysis for Hypotheses 2a-d.** These hypotheses will be tested using ANCOVA models to compare groups (BEST vs. control) for each of main outcome measured at post-treatment, after adjusting for baseline measurement of the outcome as a covariate. Compared to a "split-plot ANOVA" or an analysis of change scores, this strategy offers greater statistical power and better controls for possible baseline differences.

**Power Analysis for Hypotheses 2a-d. Table 7** shows the required sample size as a function of the standardized effect size and the correlation between posttest and baseline scores to achieve 80% power using a two-tailed alpha of 0.05. Cohen describes an effect size of d=0.8 as large, d=0.5 as medium, and d=0.2 as small. **Table 7** focuses on the combination of effect sizes and pretest-posttest correlations that would achieve power of .80. To evaluate plausible pretest-posttest correlations for the measures associated with hypotheses 2a-c, we assessed baseline to 4-month follow-up measures in a RCT of a sleep intervention for Veterans with disabilities. These are presented in detail below for each of the three hypotheses. **Table 7** shows that under the most pessimistic scenario (assuming no correlation between pre-test and post-test measures), this study has sufficient power to detect a large effect (*d*=0.75). As the purpose of this study is to find clinically meaningful effects (i.e., effects that tend to be large), this power analysis suggests sufficient power to detect such effects for all outcome measures. However, our prior research found very substantial pretest/posttest correlations (e.g., r=.75) which would permit detection of smaller effects (i.e., medium effects of d=0.50). Using the lower confidence limits still found substantial correlations (e.g., r=0.56) suggesting that this study will have the ability to detect all effects of d=0.63 or larger with a sample size of n=56 with complete 3-month follow-up data. To achieve this, we will randomize 62 subjects into intervention vs. control.

**Table 7**. Required total sample size as afunction of effect size and pre-test/post-testcorrelation for 80% power, alpha=.05.

Sample	Effect Size	Pretest/Posttest
Size	(Cohen's d)	Correlation
	d=0.50 (medium)	r=0.75
N=56	d=0.55	r=0.68
N-50	d=0.60	r=0.60
	d=0.63	r=0.56

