Hypothesis 2a: To estimate the pretest-posttest correlation, we used our prior research showing a baseline-4-month correlation for PSQI of r=0.74 (95% CI=[.56,.86], N=40). Choosing

d=0.65	r=0.50
d=0.70	r=0.36
d=0.75	r=0.00

the lower confidence limit (r=.56) implies sufficient power to detect an effect size of Cohen's d=.63 (an effect somewhat larger than a medium effect) with N=56 (**Table 7**). Choosing the observed correlation (r=.74) implies sufficient power to detect an effect size of Cohen's d=.50 (a medium effect). Assuming no correlation (r=0.00), the study could still detect an effect size of Cohen's d=.75 (a large effect).

Hypothesis 2b: In the same preliminary data we found the baseline-4-month correlation of instrumental measures of daily living (IADLs) was r=.81 (95% CI=[.67, .89[). Using the lower confidence limit suggests the ability to detect an effect of d=.55 (slightly larger than medium effect).

Hypothesis 2c: To inform the power for this hypothesis, we examined baseline-4-month correlations for PHQ9 and FSS in our prior work. The correlation for PHQ9 was r=.79 (95% CI=[.64,.89], N=40), and for FSS, r=.76 (95% CI=[.57,.87], N=36). Using a conservative approach (lowest lower confidence interval = 0.57), an effect size of 0.63 could be detected with a sample size of 56 (See **Table 7**). Assuming the lowest observed correlation (r=0.76), the study would have sufficient power to detect an effect of d=0.50 (a medium effect). Our **Preliminary Data** shown in section 3.6 indicate large treatment effects comparing a behavioral sleep program vs. attention-control in terms of FSS ( $\omega^2$ =64%) and PHQ9 ( $\omega^2$ =35%). We believe similarly "large" effects for these outcomes are likely in the proposed study.

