Hypothesis 2d: The main respiratory function outcomes are PFTs (i.e., upright and supine respiratory function/forces) measured at 3-months. While we have no prior data on pretest/posttest correlations for these measures, our prior research has found a the SD for FVC when measured sitting is 17.1, and 15.7 when supine. Considering a 12% change as clinically relevant, this implies an improvement, expressed as Cohen's d=.70 (sitting, 12/17.1) and d=.76 (supine 12/15.7). **Table 7** shows that there would be sufficient power to detect a 12% improvement in sitting respiratory function (corresponding to d=.70) given a correlation of r=.36 in from baseline to 3 months. Likewise, there would be sufficient power to detect a 12% improvement in supine respiratory function (corresponding to d=.76) regardless of the size of the correlation.

4.6d: Analysis plan for Exploratory Aim 3: This aim considers whether the BEST program is more effective for subgroups of patients such as those with depression, insomnia or bladder dysfunction. For categorical measures, grouping variables will be coded as 0/1. For continuous measures (such as ISI score), participants will be categorized into groups, using clinical cutoffs. If such cutoffs yield highly imbalanced groupings, we will consider a median split. For a given variable, each grouping variable will be interacted with treatment group and introduced into each analysis described in Aims 1 and 2. The test of the interaction will assess whether the treatment is more effective for one subgroup than another.

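### The protocol's claim that 56 complete participants detect every Aim 2 effect of d=0.63 or more is too broad: it lacks support for WHOQOL-BREF, ESS, FVC and MIP, and rests on a proxy for functional status

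*Protocol*

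**What the plan says.** Protocol section 4.6a (overview of sample size computations) says that Aim 2 needs the largest sample and so sets the size of the trial: 56 complete, 62 randomized. Under the power analysis for Hypotheses 2a-d, section 4.6c tests each outcome by ANCOVA with the baseline score as covariate. Table 7 gives the effect sizes and correlations with which 56 participants suffice "to achieve 80% power using a two-tailed alpha of 0.05". The text first says that with no correlation a large effect, d=0.75, is detectable for all outcome measures. It then turns to the lower confidence limits of earlier correlations and concludes that "this study will have the ability to detect all effects of d=0.63 or larger with a sample size of n=56".

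The correlations come from an earlier trial in Veterans with disabilities and are introduced for Hypotheses 2a-c only:

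- **2a, sleep quality:** PSQI, r=.74, lower limit .56.
- **2b, functioning:** "In the same preliminary data we found the baseline-4-month correlation of instrumental measures of daily living (IADLs) was r=.81", lower limit .67, from which d=.55 is derived.
- **2c, quality of life:** "To inform the power for this hypothesis, we examined baseline-4-month correlations for PHQ9 and FSS in our prior work". PHQ-9 has r=.79, lower limit .64. Fatigue has r=.76, lower limit .57.
- **2d, respiratory function:** "While we have no prior data on pretest/posttest correlations for these measures". The text works instead at d=.70 (sitting FVC, if r=.36) and d=.76 (supine FVC, at any r).

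The outcome definitions in section 4.4d differ from these inputs in places. For quality of life, "The four WHOQOL-BREF domain scores will be used as main outcome measure". Functional status is SCIM-SR. Supine FVC and MIP are the key respiratory outcomes. The SAP measures functional status by CHART, adds sleepiness (ESS) to Aim 2, and gives a two-sample t-test for each outcome.

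**The concern.** The underlined sentence stands under a heading that covers all four hypotheses and says that all effects of the stated size are detectable. It is also the sentence from which the 62 randomized participants follow. Yet d=0.63 is one row of Table 7, and that row needs a correlation of .56. Several outcomes have no estimate of this correlation, and one borrows it from an instrument the trial does not use. MIP has no SD, effect size or power figure at all.

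What is at stake is the operating characteristic that readers will attach to each outcome. Someone reading a null result on a WHOQOL-BREF domain or on MIP would take the chance of missing d=0.63 to be 20%. With no correlation it is about 36%.

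**Working it through.** **Inputs** (Protocol 4.6a and 4.6c): two-sided alpha .05, 80% power, 28 per group with complete data, ANCOVA on baseline, and the correlations listed above.

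**Formulae.** ANCOVA reduces the residual SD by the factor √(1−r²), so the effective effect is d/√(1−r²).
- Normal approximation: detectable d = (1.960 + 0.842) × √(2/28) × √(1−r²) = 0.749 × √(1−r²).
- t-based power: noncentral t, noncentrality [d/√(1−r²)] × √(28/2), 53 degrees of freedom.

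**Reproducing Table 7.** All seven rows return N=56 by the normal approximation, with power of 80.1% to 81.2% (78.7% to 79.8% by noncentral t). Two rows in full:
- r=.56: √(1−.3136) = .828, and 0.749 × .828 = 0.620, so d=0.63 is met.
- r=0: 0.749, tabulated as 0.75. The unadjusted t-test gives 0.762.

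**Correlation needed for d=0.63.** √(1−(0.63/0.749)²) = .54 by the normal approximation, and about .56 t-based.

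**Detectable d at the protocol's lower limits (normal approximation).**

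| Measure with an estimate | Lower-limit r | Detectable d |
|---|---|---|
| PSQI | .56 | 0.620 |
| Fatigue | .57 | 0.615 |
| PHQ-9 | .64 | 0.575 |
| IADL (proxy for functional status) | .67 | 0.556 |

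All four are below 0.63.

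**Outcomes without their own correlation.** WHOQOL-BREF, ESS, FVC and MIP have none, so r is an assumption and is shown as a range. The d=.55 column applies to functional status if the IADL value does not carry over.

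| Assumed r | Power at d=0.63, t-based (normal) | Power at d=.55, t-based (normal) |
|---|---|---|
| 0 | 64% (65%) | 52% (54%) |
| .30 | 68% (70%) | 56% (58%) |
| .50 | 76% (78%) | 65% (66%) |
| .56 | 80% (81%) | 68% (70%) |
| .67 | 88% (89%) | 78% (79%) |

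**FVC.** 12/17.1 = 0.70 sitting and 12/15.7 = 0.76 supine, as the protocol says. At r=0, power for d=0.76 is about 80% (t-based) or 81% (normal), so the supine claim stands without any correlation. The sitting claim at d=0.70 has 73% (t-based) at r=0 and needs the r=.36 that the protocol states as its condition.

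**SAP analysis.** If the two-sample t-test compares 3-month scores without the baseline covariate, r drops out. The detectable effect is then d=0.76 for every outcome, and power at d=0.63 is 64%.

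**The case against.** The strongest reply is that the paragraph already contains the answer. It states d=0.75 with no correlation for all outcome measures, Table 7 has that row, and d=0.63 follows as a second scenario built on data said to concern Hypotheses 2a-c. Respiratory function is treated separately and does not rely on d=0.63. This stands, and it limits the fault to the scope of one sentence. It does not remove the fault, because the protocol gives both d=0.75 and d=0.63 without saying which outcomes each covers.

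A second reply is that r=0 is a worst case. Every correlation reported is .74 to .81, and borrowing from related scales is ordinary planning. That is fair, and it is why the results are shown over a range of r. The true correlation for WHOQOL-BREF or MIP may well exceed .56, but the documents do not show it.

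Third, ESS has no aim number in the protocol's Table 6 and enters Aim 2 only through the SAP, which makes no power claim. This also stands. ESS needs a figure only if it remains an Aim 2 outcome.

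Four stronger readings are tempting, and the documents do not support them:

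- **Functional status has no correlation input.** It has one, the IADL estimate. The weakness is that neither document links it to SCIM-SR or CHART.
- **The sample size arithmetic is wrong.** Table 7 reproduces in full.
- **The trial must be enlarged.** Detecting d=0.63 at r=0 would take 80 complete participants (82 by t-test), but the plan accepts d=0.75 in the no-correlation case.
- **The plan would read a null result as excluding d=0.63.** Nothing in either document says so, and a confidence interval would settle that question.

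**Conclusion.** The sentence is too broad for Hypotheses 2a-d. With baseline-adjusted ANCOVA and 28 complete per group, d=0.63 is supported directly for PSQI, PHQ-9 and fatigue. For functional status, d of about .55 is supported only if the IADL correlation carries over; otherwise the detectable effect can be as large as 0.75. For WHOQOL-BREF domains, ESS, FVC and MIP the supported figure is d=0.75 (about 0.65 if r were .50), and power at d=0.63 is about 64% to 76% for r between 0 and .50.

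This rests on three assumptions: the lower confidence limits are reasonable planning values; the scale abbreviated FSS in the power section is the Flinders scale (section 4.4d uses both FFS and FSS for it); and the Aim 2 analysis adjusts for baseline. If the last fails, d=0.76 applies throughout. The matter is one of stated power, to be corrected in the text. It does not affect the number of participants.

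**What to change.** In Protocol section 4.6c, replace the underlined claim with a statement by outcome, for example:

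*With baseline-adjusted ANCOVA and 56 complete participants, the study has about 80% power for d=0.63 on PSQI, PHQ-9 and fatigue; for d=.55 on functional status if the IADL correlation carries over to the instrument used, otherwise up to d=0.75; and for d=0.75 on WHOQOL-BREF domains, ESS, FVC and MIP (about d=0.65 if r=.50). Under an unadjusted two-sample t-test of 3-month scores the detectable effect is about d=0.76 for every Aim 2 outcome.*

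Make the d=.55 given under Hypothesis 2b conditional in the same way, and name the functional status instrument to which it refers. State in the SAP whether the Aim 2 comparison adjusts for the baseline score, so that the power statement and the analysis agree.

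The cost is a rewording of section 4.6c and one sentence in the SAP. Table 7 stays as it is and no patients are added. The stated detectable effect becomes less favourable for the outcomes without their own correlation.
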